The INSPIRE-ASP Trial (INtelligent Stewardship Prompts to Improve Realtime Empiric Antibiotic Selection for Patients) for Skin and Soft Tissue (SST) Infections Statistical Analysis Plan

> NCT:05423756 3/29/2024

Statistical Analytic Plan, 3/29/2024

[name]

Background

The INSPIRE Skin and Soft Tissue (SST) Infections Trial (INtelligent Stewardship Prompts to Improve Real-time Empiric Antibiotic Selection for Patients with Skin and Soft Tissue Infections) is a cluster-randomized trial of HCA Healthcare (HCA) affiliated hospitals to determine whether antibiotic prescribing practice for adult hospitalized patients admitted to non-critical care units with skin and soft tissue (SST) infections can be affected by providing physicians with individualized risk estimates for whether a patient with an SST infection is likely to have an antibiotic-resistant infection. It compares routine care to a real-time smart prompt to use a standard-spectrum antibiotics when a physician orders an extended-spectrum antibiotic (ES) for a patient whose risk of antibiotic resistant infection is low (<10%). The main goal is to see if there is a difference in the empiric antibiotic prescribing practices for ES. The term "antibiotics" refers to antibacterial antibiotics in this trial. We define antibiotics administered during the first three days of hospitalization as empiric treatment because infecting pathogens and their antimicrobial susceptibilities are typically not known during this period. We refer to these first three days as the empiric period.

Extended-spectrum antibiotics are defined in Table 1 below.

Table 1: Extended-Spectrum Antibiotics in the INSPIRE-ASP Skin and Soft Tissue Infections Trial

Category	Extended-Spectrum Antibiotics for INSPIRE CPOE Alerts	
Anti-VRE	Daptomycin, Linezolid ¹ , Tigecycline	
Anti- Pseudomonals	Aztreonam, Cefepime, Ceftazidime, Piperacillin/tazobactam	
Anti-ESBL	Ertapenem, Imipenem, Meropenem, Ceftolozane/tazobactam	
Anti-CRE Ceftazidime/avibactam, Imipenem/relebactam, Meropenem/vaborbactam, Polymixin B, Colistin, Tigecycline		

¹Both oral and intravenous (IV) formulations

Note: Does not include aminoglycosides or fluoroguinolones.

Abbreviations: **MRSA** - Methicillin Resistant *Staphylococcus aureus*; **VRE** - Vancomycin Resistant *Enterococci*; **ESBL** - Extended Spectrum Beta Lactamase producer; CRE - Carbapenem Resistant Enterobacteriaceae

Participating hospitals are randomized to:

- Arm 1 Routine Care
- Arm 2 Real-Time Risk Estimation Smart Prompt

Computerized physician order entry (CPOE) prompt that recommends standard-spectrum antibiotics in patients admitted for SST infections who are prescribed extended-spectrum antibiotics and calculated to have low risk (<10%) for an antibiotic resistant infection.

Trial Outcomes

Table 2: Primary and Secondary INSPIRE-ASP Skin and Soft Tissue Infections Trial Outcomes

Outcome	Metric			
Primary Trial Outcome				
Total Empiric Extended-Spectrum Antibiotic Days of Therapy (ES-DOT)	The number of different extended-spectrum antibiotics received by the patient each empiric day, summed across the first 3 days of hospitalization. ¹			
Secondary Trial Outcome				
Total Empiric Antipseudomonal Antibiotic Days of Therapy	The number of different antipseudomonal antibiotics received by the patient each empiric day, summed across the first 3 days of hospitalization. ¹			

¹E.g., if a patient is admitted for 2 days, ES-DOT will be calculated across those 2 days; however if a patient is admitted for 4 days, only the first 3 days will be evaluated.

Safety outcomes planned for the primary manuscript are shown in Table 3. Length of stay and days to ICU transfer are evaluated within 14 days of admission since empiric antibiotic selection within the first 3 hospital days is not expected to be the main driver of either outcome beyond this time; evaluation of baseline data also shows that 91% of patients with skin and soft tissue infections have length-of-stay equal to or less than 14 days.

Table 3: Other Pre-Specified Outcomes – Trial Safety Outcomes

Safety Trial Outcomes (other pre-specified outcomes)				
ICU Transfer [Safety Outcome]	Days to ICU transfer, between hospital days ≥ 3 and ≤ 14.			
Length-of-stay [Safety Outcome]	Days from hospital admission until discharge or hospital day 14, whichever comes first, where admission day is hospital day 1.			

Data Collection Details

The trial will be assessed among the cohort of adult admissions who: 1) have administrative claims codes indicating an SST infection is present on admission; 2) received any antibiotic within 3 days of admission; and 3) were admitted to a non-ICU location.

The rationale for including only the first three days of the admission is that this is when the actual status of the patient with respect to the need for an ES antibiotic is unknown. Bearing this in mind, antibiotics given during an associated emergency department visit on the date of hospital admission are counted toward the ES-DOT of the first hospital day.

The trial baseline period includes January 1, 2019 – December 31, 2019 (12 months). The intervention period includes January 1, 2023 – December 31, 2023 (12 months). The baseline was selected to include time prior to the arrival of the COVID-19 pandemic since hospital operations and case mix were dramatically affected between Winter 2020-Spring, 2022. ¹⁻⁴ Although COVID-19 surges have continued to occur, clinical operations and patient case mix at most hospitals have largely returned to near pre-pandemic activity. We considered that a state of pre-pandemic normalcy returned by summer of 2022, and introduced our intervention on August 2, 2022. The period between then and December 31, 2022 is considered a phase-in period and is not used in trial evaluation.

Primary Statistical Analysis

The primary trial outcome is defined as the summed number of different ES antibiotics received during each empiric day, on the patient-admission level. An empiric day is a day within the first three days of an admission. We define this outcome as the Total Empiric Extended-Spectrum Days of Therapy (ES-DOT). For clarity, the calculation is as follows: we define a DOT for a particular ES antibiotic as a day in which any number of doses of that antibiotic is given. Different

ES antibiotics are summed within each empiric day for each patient admission to determine DOT in that at-risk day.

The main trial results will be based upon as-randomized, unadjusted analyses of admission-level ES-DOT. We note that the national DOT measure defined by CDC is measured at the hospital level. We define ES-DOT at the individual admission level so that we can perform analyses on individuals.

The main evaluation of all outcomes will be based on the difference in differences between the intervention and baseline periods and between study arms.

The unit of analysis will be individual admissions. Individual patients can contribute more than one admission. The analytic model will be a generalized linear mixed effects model for differences in differences, with random effects to account for correlation within hospital between period, within hospital within period between patient, and within patient between admission. We plan to use a Poisson model for analysis of outcomes as follows:

 $log(y_{ijph}) = \beta_0 + \beta_1 A_{ijph} + \beta_2 T_{ijph} + \beta_3 A_{ijph} T_{ijph} + b_{0h} + b_{1h} T_{ijph} + g_j + \log{(ed_j)}$ where y_{ijph} is the ES-DOT for patient i for admission j in period p at hospital h, and $A_{ijph} = 1$ if hospital h is in the intervention arm and 0 if not, and $T_{ijph} = 1$ if p is the intervention period and 0 if baseline period. The random effects b_{0h} and b_{1h} allow for different baseline mean admission-level ES-DOT for each hospital and each hospital in the intervention period, respectively. Equivalently, they allow for correlation within hospital at different levels at baseline and at follow-up. The random effect g_j allows each patient to have a different mean ES-DOT. Finally, ed_j is the number of empiric days in the admission. We note that it may not be possible to fit models with the g_j parameter, for various numerical and computational reasons—the most prominent being a relative sparsity of patients with readmissions. If that proves to be the case, we will randomly select one admission per patient and use the model above without that parameter and omitting the j subscript.

The assessment of trial success will be determined by assessing the significance of the arm by period interaction term β_3 , which estimates the log relative rate of the outcome due to being in the intervention arm in the intervention period. The exponentiated parameter estimate for β_3 is the estimated relative rate of ES-DOT per at-risk day due to the intervention, relative to the baseline period. For example, if β_3 had a negative value and a p-value <0.05, we would conclude that the patient-specific CPOE smart prompts generated a benefit over routine care. Exponentiating the parameter value would provide an estimate of the relative reduction due to the intervention in the expected ES-DOT per at-risk day.

The primary trial analysis will use an as-randomized unadjusted model with two-tailed significance set at alpha = 0.05. The secondary outcome will be assessed using an as-randomized unadjusted model with alpha = 0.05.

Subsequent analyses of the primary and secondary outcome will include both as-treated and adjusted models. Adjusted models will account for individual characteristics such as age, gender, comorbidities, and prior history of MDROs as well as hospital characteristics such as hospital antibiotic resistance. We will also account for seasonality. All adjusters will be determined a priori. These analyses will be reported as point estimates with confidence intervals and without p-values. The reason for including these analyses is to provide additional information related to the trial outcomes for readers to assess the effects of potential confounders. The reason to not include them in a formal multiple comparisons adjustment is because these analyses are non-independent evaluations relative to the as-randomized unadjusted analyses.

Safety Outcomes

Safety outcomes are required because a reduction in ES-DOT might be achieved only by incorrectly withholding ES antibiotics when they were necessary. Each safety outcome will be

evaluated for non-inferiority using an as-randomized unadjusted analysis with a one-tailed significance set at alpha = 0.05. For length of stay, the non-inferiority margin is a hazard ratio of 0.98. For days to ICU transfer, the non-inferiority margin is a hazard ratio of 1.1 (fewer days to ICU results in a hazard ratio above 1). Analyses planned for these assessments are proportional hazards models with random effects for each time period, hospital, and admission. These models are sometimes called frailty or shared frailty models. Because these are safety outcomes, we do not intend to make adjustments for multiple comparisons in testing them, further increasing conservatism. As above, it may not be possible to include multiple admissions.

All analyses will be performed using current versions of SAS/STAT and/or R packages Ime4 and coxme, unless better packages become available in the meantime.

Further Planned Analyses

We note that there are other pre-specified outcomes intended for exploratory analysis in secondary papers for the INSPIRE SST trial in Table 5 below.

Table 5: Secondary Manuscripts - Other Pre-Specified Outcomes

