Trial data will not be collected by participating sites. Instead, all variables and outcomes will be obtained from custom extractions from the HCA Healthcare computerized data warehouse. HCA Healthcare has a long-established corporate data warehouse with admission data, demographics, diagnostic and procedure codes, CPOE data, and laboratory and pharmacy data. Trial data from the computerized data warehouse will include demographic, insurer, comorbidity, and laboratory (including microbiology) data for SST infection cohorts.

G.2. Specifications of the Appropriate Outcome Measures

The primary, secondary and safety trial outcomes are summarized below in Table 3.

G.3. Primary Outcome Measures

The primary trial outcome for SST infections reflects the national metric of days of therapy (DOT) of extended-spectrum antibiotic use (ES-DOT), which we will evaluate for the empiric period (hospital day 1-3). Trial success will be based upon the relative reduction in this metric between the INSPIRE Stewardship Bundle vs routine care arm when accounting for baseline values.

G.4. Secondary Outcome Measures

There will be one secondary outcome for SST infections (antipseudomonal antibiotic days of therapy).

G.5. Safety Outcomes

Two safety outcomes will also be assessed. We will evaluate if increased use of standard-spectrum antibiotics causes increased ICU transfers or hospital length-of-stay.

Table 3. Trial Outcomes

Outcome	Metric for SST infection Cohorts
Primary Trial Outcome: Total Empiric Extended-Spectrum Antibiotic Days of Therapy (ESDOT)	The number of different extended-spectrum antibiotics each empiric day, summed across the first 3 days of hospitalization. ¹
Secondary Trial Outcomes: Total Empiric Antipseudomonal Antibiotic Days of Therapy (ES-DOT)	The number of different antipseudomonal antibiotics each empiric day, summed across the first 3 days of hospitalization. 1,2
Safety Outcomes: ICU Transfer	Intensive Care Unit (ICU) Transfer: Days to ICU transfer, from hospital days ≥ 3 and ≤ 14
and Length-of-Stay	Length-of-stay: Days from hospital admission until discharge or hospital day 14, whichever comes first, where admission day is hospital day 1.

¹E.g., if a patient is admitted for 2 days, ES-DOT will be calculated across those 2 days; however if a patient is admitted for 4 days, only the first 3 days will be evaluated.

H. Statistical Considerations

H.1. Criteria for Discontinuation or Withdrawal

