where y_{ijph} is the ES-DOT for patient i for admission j in period p at hospital h, and $A_{ijph}=1$ if hospital h is in the intervention arm and 0 if not, and $T_{ijph}=1$ if p is the intervention period and 0 if baseline period. The random effects b_{0h} and b_{1h} allow for different baseline mean admission-level ES-DOT for each hospital and each hospital in the intervention period, respectively. Equivalently, they allow for correlation within hospital at different levels at baseline and at follow-up. The random effect g_j allows each patient to have a different mean ES-DOT. Finally, ed_j is the number of empiric days in the admission.

ES-DOT. Finally, ed_i is the number of empiric days in the admission. The assessment of trial success will be determined by the significance of the arm by period interaction term β_3 , which assesses whether the log relative rate of the outcome due to being in the intervention arm in the intervention period is different from 0. The exponentiated parameter estimate for β_3 is the estimated relative rate of ES-DOT per at-risk day due to the intervention, relative to the baseline period. For example, if β_3 had a negative value and a p-value <0.05, we would conclude that the patient-specific CPOE smart prompts generated a benefit over routine care. Exponentiating the parameter value would provide an estimate of the relative reduction due to the intervention in the expected ES-DOT per at-risk day.

The primary trial analysis will use an as-randomized unadjusted model with two-tailed significance set at alpha = 0.05. Secondary outcomes will be assessed using an as-randomized unadjusted model and will include adjustment for multiple comparisons with two-tailed significance set at alpha = 0.025 for the two secondary outcomes.

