Subsequent analyses of the primary and secondary outcomes will include both as-treated and adjusted models. Adjusted models will account for individual characteristics such as age, gender, comorbidities, and prior history of MDROs as well as hospital characteristics such as hospital antibiotic resistance. We will also account for seasonality. All adjusters will be determined a priori. These analyses will be reported as point estimates with confidence intervals and without p-values. The reason for including these analyses is to provide additional information related to the trial outcomes for readers to assess the effects of potential confounders. The reason to not include them in a formal multiple comparisons adjustment is because these analyses are non-independent evaluations relative to the as-randomized unadjusted analyses.

We will separately evaluate intervention period effects by arm alone.

Safety Outcomes

Safety outcomes noted in the above table will be assessed in the most conservative manner to identify potential safety issues. Safety outcomes are required because a reduction in ES-DOT might be achieved only by incorrectly withholding ES antibiotics when they were really needed. Each safety outcome will be evaluated for non-inferiority using an as-randomized unadjusted analysis with a one-tailed significance set at alpha = 0.05. Length-of-stay and days to ICU transfer are evaluated within 14 days of admission since empiric antibiotic selection within the first 3 hospital days is not expected to be a main driver of either outcome beyond this time period; evaluation of baseline data also shows that 91% of SST patients have length-of-stay equal to or less than 14 days. Analyses planned for these assessments are proportional hazards models with random effects for each hospital and admission These models are sometimes called frailty or shared frailty models. Because these are safety outcomes, we do not intend to make adjustments for multiple comparisons in testing them, further increasing conservatism.

All analyses will be performed using current versions of SAS (Version 9.4, as of writing, SAS Institute, Cary NC) and/or R (Version 4.0, as of writing).

C.2.11 Power Size/Sample Size Calculations

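### Protocol and SAP give different thresholds for the one secondary outcome, unadjusted non-inferiority tests are wrongly called more conservative, and the two safety power figures do not say what they are power for

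*SAP*

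**What the plan says.** **Secondary outcome.** Protocol G.4 states: "There will be one secondary outcome for SST infections (antipseudomonal antibiotic days of therapy"). Protocol Table 3 lists that one outcome, and SAP Table 2 lists it again as "The number of different antipseudomonal antibiotics received by the patient each empiric day, summed across the first 3 days of hospitalization". Yet Protocol H.3 plans "adjustment for multiple comparisons with two-tailed significance set at alpha = 0.025 for the two secondary outcomes". The SAP (Primary Statistical Analysis) has instead: "The secondary outcome will be assessed using an as-randomized unadjusted model with alpha = 0.05".

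**Safety outcomes.** Both documents test length of stay (margin: hazard ratio 0.98) and days to ICU transfer (margin: hazard ratio 1.1) for non-inferiority, each at one-tailed 0.05. The Protocol says the safety outcomes will be "assessed in the most conservative manner to identify potential safety issues". Both documents defend the lack of a multiplicity correction in the same terms; the SAP's sentence is: "Because these are safety outcomes, we do not intend to make adjustments for multiple comparisons in testing them, further increasing conservatism".

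**Power.** The Protocol's Power Size/Sample Size Calculations section says that the trial was sized on its power for the safety non-inferiority comparisons. It then gives 68.9% (CI 65.9-71.8%) as the power to identify stays lengthened by a day or more in 12.5% of patients with stays under 14 days. For ICU transfer it gives more than 99.9% (CI 99.6-99.9%) as the power to detect a 2% rise on days 3 to 14. Each figure is followed by a non-inferiority margin.

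**The concern.** The secondary result could be declared a success or a failure depending on which document is followed.

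For safety, the type I error of a non-inferiority test is a false declaration of safety. Leaving out an adjustment cannot make that error rarer. The stated reason fits a test that looks for harm, which is the aim the Protocol announces but not the test it plans.

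The Protocol itself says that adoption will depend heavily on showing safety. A reader needs the chance that the trial concludes non-inferiority if the prompts are in truth safe, and cannot tell whether either safety power figure is that chance.

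**Working it through.** **1. Secondary threshold.** 0.05 / 2 = 0.025 reproduces the Protocol's alpha for two outcomes. For the single outcome defined, 0.05 / 1 = 0.05, which is the SAP's value. The error is the count in Protocol H.3 and the alpha derived from it.

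**2. Direction of the safety error.** Each test at its own margin has a 5% chance of a false non-inferiority conclusion. If an overall claim requires both outcomes to pass, the joint error is at most 5% with no adjustment. Omitting the adjustment is then neutral. Under no rule is it more conservative.

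**3. Length-of-stay power.** The 68.9% came from a bootstrap of hospital data that are not in the documents, so the figure itself cannot be reproduced. Its interval can: 689 successes in 1,000 simulations (number assumed) give an exact 95% interval of 65.9 to 71.8%, and 1,000 in 1,000 give a lower limit of 99.6%, as printed for ICU transfer.

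Inputs: about 61,000 patients (Protocol, Brief Overview); 91% with stays of 14 days or less (Protocol H.3, Safety Outcomes); margin 0.98; one-sided 0.05 (z = 1.645).

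- *Hazard ratio in the scenario.* Assumed shapes are exponential, Weibull (shape 0.9 and 1.3) and lognormal (median 4, 5 and 6 days), each in whole days and fitted to 91% by day 14. Add exactly one day, the mildest reading, to 12.5% of stays under 14 days. The Cox hazard ratio is 0.974 to 0.981, depending on shape, tie handling and whether day-14 discharges count as events.
- *Standard error of log HR.* 2/√(61,000 × 0.91) = 2/√55,510 = 0.00849 for the intervention period only. For difference-in-differences with an assumed equal-sized baseline, multiply by √2 to get 0.0120.
- *Power to conclude non-inferiority:* Φ((ln HR − ln 0.98)/SE − 1.645).
- *Power to detect harm:* Φ(−ln HR/SE − 1.645).

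| True HR | Power for | Intervention period only | Difference-in-differences |
|---|---|---|---|
| 0.981 | non-inferiority | 6.4% | 5.9% |
| 0.9735 | non-inferiority | 0.8% | 1.4% |
| 0.981 | detecting harm | 73% | 48% |
| 0.9735 | detecting harm | 94% | 72% |
| 1 | non-inferiority | 77% | 52% |

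The first two rows exclude 68.9%. Detecting harm (48 to 94% over both designs) and non-inferiority at HR 1 (52 to 77%) both span it.

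**4. ICU power.** The documents give no transfer rate.

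- *If 2% is relative (HR 1.02).* Events needed for non-inferiority power of 99.6 to 99.9% are 4 × ((1.645 + z)/ln(1.1/1.02))², about 12,950 to 15,730. That is 21 to 26% of 61,000 for the intervention period only, and twice as many events under the difference-in-differences approximation. Detecting HR 1.02 as harm would need about 188,000 to 229,000 events, more than all patients.
- *If 2% is percentage points.* HR = ln(1 − r − 0.02)/ln(1 − r), which is 3.03, 1.42, 1.21 and 1.11 at assumed baseline rates r of 1%, 5%, 10% and 20%. It falls to 1.1 only at r = 23.2%. At any lower rate the scenario lies beyond the margin, so the figure could not be power to conclude non-inferiority under it.

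The two readings describe different quantities, and the text does not choose between them.

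**The case against.** Much can be said for the plan. Every place except Protocol H.3 agrees on one secondary outcome, and the later SAP carries the matching alpha. The SAP sentence just before it says two-tailed, so two-sided is the natural reading. Each safety outcome is to be evaluated on its own, which needs no correction. The Protocol does name its power scenarios, and recalculated power cannot change the size of a trial whose intervention period ended in 2023; the confidence intervals will show whether the margins are met. All of this stands. It limits the point to one conflicting threshold, one wrong reason and two unlabelled figures.

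Four stronger readings are tempting and are not supported:

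- *That the chance of a false safety claim is 9.75% (1 − 0.95²).* That would need a rule that either outcome alone suffices, and independent tests. The documents state no such rule.
- *That 68.9% must be power to detect harm.* Non-inferiority power at HR 1 fits it as well.
- *That the threshold was relaxed after results were seen.* The SAP is dated 3/29/2024, after the intervention period, but the documents do not say whether outcome data had been examined.
- *That none of the power statements can be interpreted.* The ES-DOT statement is clear: power for a 12.5% relative reduction.

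**Conclusion.** The point holds in three limited parts. The secondary thresholds differ twofold (0.025 against 0.05, taking the SAP's test as two-sided), and this is a plain contradiction. The conservatism remark is wrong as a reason, but the planned safety tests are acceptable. The 68.9% is not the power to conclude non-inferiority in the scenario it accompanies, which is about 1 to 6%; what it does represent cannot be settled from the documents, and the ICU figure is ambiguous in the same way.

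The power results rest on assumed length-of-stay shapes, exactly one added day, a baseline as large as the intervention period, and no clustering. Clustering would change them, and would lower the 52 to 77% at HR 1. The first two parts need no assumption beyond the two-sided reading.

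**What to change.** - **Protocol H.3:** change to one secondary outcome at two-sided 0.05, matching the SAP. Add the word two-sided to the SAP sentence, and record when and why the threshold changed.
- **Safety Outcomes, both documents:** delete the closing remark about conservatism and report each outcome against its own margin. If an overall safety claim is to be made, state that it requires both margins to be met.
- **Protocol power section:** for each safety figure, say whether it is power to conclude non-inferiority or to detect harm, give the true hazard ratio assumed, and say whether 2% is relative or in percentage points. Restate the power to conclude non-inferiority under no true difference by rerunning the existing bootstrap with no effect imposed and the planned difference-in-differences model.

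The cost is a few sentences in each document and one simulation rerun. No planned test changes and no new data are needed. The downsides are that the restated length-of-stay power may look modest, as the last row of the table suggests, and that if an overall claim requires both margins, a split result supports only an outcome-specific statement.
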